5.1.7 Accelerated elimination of teriflunomide and duration of continued contraception

Approximately half of the subjects in the core study received teriflunomide as their study treatment, but due to blinding, all subjects will undergo an accelerated elimination procedure followed by an assessment of compliance to the elimination procedure prior to administration of the first dose of ponesimod in the extension study.

During the early stages of the study (protocol versions 1 through 4), additional plasma teriflunomide tests may have been required to confirm that teriflunomide plasma levels were sufficiently low (<0.02 mg/L) before fertile male participants could stop contraceptive requirements and in the case of planned pregnancies (see Section 5.1.12.5). Following approval of

15 March 2022, page 67/216

Confidential

EudraCT 2016-004719-10 EDMS-ERI-207656619

protocol version 5, these tests are no longer required now that all ongoing subjects have been off teriflunomide for over 2 years (last subject entered this extension study on 20-May-2019) [Aubagio® USPI, Aubagio® SmPC].

5.1.8 Study treatment dose adjustments and interruptions

Study treatment up-titration, other than described in Section 5.1.2, is prohibited. Study treatment down-titration is not foreseen in any situation and is prohibited.

Study treatment interruption should be avoided. If study treatment intake is interrupted by the subject for any reason, she/he must immediately inform the investigator / treating neurologist.

Study treatment may be temporarily interrupted in response to an AE, a diagnostic or therapeutic procedure, a laboratory abnormality, vaccination (see Section 5.2.3), or for administrative reasons. Study-specific criteria for interruption of study treatment are described in Section 5.1.12. The permitted maximum duration of the study treatment interruption is 81 weeks for planned pregnancies and 12 weeks for other reasons (if exceeded, the subject will then be prematurely discontinued from the study).

Detailed guidance on how to re-initiate study treatment in the event of drug interruption is provided in Section 5.1.9.

Study treatment dose interruptions must be recorded in the eCRF.

5.1.9 Guidance for re-initiation of study treatment in the event of study treatment interruption

If study treatment intake (up-titration or maintenance phases) is interrupted by the subject for any reason, she/he must immediately inform the principal investigator / treating neurologist.

The following guidance is provided for re-initiation of investigational study treatment after study treatment interruptions.

A schematic overview of the re-initiation algorithm is given below in Figure 2.

Depending on the day, time, and duration of study treatment interruption, the following procedures will be followed.

- If the subject missed taking the dose in the morning:
 - The dose should be taken at any time on the same day.
 - Regular dosing should be resumed with the morning dose on the following day.
- If the subject missed taking the dose for up to three consecutive days:
 - Dosing should be resumed in the morning, with the same dose taken prior to study treatment interruption.
 - Study treatment intake may be re-initiated by the subject at home.

15 March 2022, page 68/216

Confidential

- Subjects must be instructed to contact the investigator immediately if they experience any symptoms of bradycardia (e.g., dizziness, vertigo, syncope).
- If the subject missed taking the dose of ponesimod for four or more consecutive days, then the original up-titration scheme for the investigational study treatment needs to be re-applied.
- 1. Subjects with cardiovascular risk factors (i.e., meeting any of the below-listed Criteria for Cardiac Monitoring at Site) will require cardiac monitoring and therefore must have their reinitiation of study drug performed at the site. On the day of the re-initiation of ponesimod, the subject must be monitored for at least 4 hours post-dose, following the cardiac assessment schedule and applying the discharge criteria as described in Section 5.1.10.

Criteria for Cardiac Monitoring at Site (cardiovascular risk factors):

- Sinus bradycardia HR <55 bpm
- History or presence during the study of first or second-degree Mobitz type I AV block
- History or presence during the study of myocardial infarction or heart failure

[figure not shown]
In the event of a re-initiation, the treating neurologist may consult with the first-dose administrator and/or a cardiologist to determine the most appropriate monitoring strategy. Cardiology advice should be sought in case of history or presence during the study of the following conditions or abnormalities:

- Atrial flutter, fibrillation or any other arrhythmias treated with anti-arrhythmic drugs;
- Unstable ischemic heart disease or cardiac decompensated failure;
- Cardiac arrest or cerebrovascular disease (e.g., transient ischemic attack, stroke);
- Mobitz Type II second-degree heart block, sick sinus syndrome or sino-atrial heart block;
- Subjects receiving concomitant therapy with drugs that decrease HR (e.g., beta-blockers, calcium channel blockers and other drugs that may decrease HR).
- 2. Subjects who do not meet any of the Criteria for Cardiac Monitoring at Site (as confirmed at pre-dose ECG assessment) may either re-initiate the study drug at home after receiving uptitration kit from the site or re-initiate study drug at site and be monitored for at least 4 hours post-dose at the discretion of the investigator / treating neurologist (see Section 8.5.3). Subjects re-initiating study drug at home must be instructed to contact the investigator or local

15 March 2022, page 69/216

emergency facilities immediately if they experience any cardiac adverse effects including symptoms of potential bradycardia (e.g., dizziness, vertigo, syncope). The additional visit 14 days (± 1 day) after the day of re-initiation (Day 15) (see Section 8.5.3) may be scheduled at the discretion of the investigator / treating neurologist.

Figure 2 Algorithm for management of treatment interruptions

^{*}Patients without cardiovascular risk factors may either re-initiate study drug at home, or at site and be monitored for at least 4 hours post-dose at the discretion of the investigator / treating neurologist.

Whenever the investigator / treating neurologist becomes aware that the subject did not report having missed the study treatment intake for one or more days during up-titration or four or more days during maintenance and has continued dosing, the subject should be interviewed by the investigator / treating neurologist for any symptoms related to bradycardia, and further examinations (e.g., 12-lead ECG, BP measurement) may be performed at the discretion of the investigator / treating neurologist. Based on an assessment of the clinical findings and the likelihood of subject's adherence to treatment, the investigator / treating neurologist will determine whether the subject can continue regular dosing, needs to re-initiate treatment, or should permanently discontinue treatment.

15 March 2022, page 70/216

EudraCT 2016-004719-10 EDMS-ERI-207656619

Confidential

5.1.10 Criteria for discharge from cardiac monitoring on Day 1, and on the first day of re-initiation of the investigational study treatment following treatment interruptions

At the time of discharge from cardiac monitoring (i.e., when the evaluation of the pre-dose and all the hourly post-dose ECGs until 4 hours post-dose have been obtained) on Day 1, and on the first day of re-initiation of study treatment following drug interruptions, the following criteria must be met:

- ECG-derived resting HR >45 bpm, and if HR <50 bpm it must not be the lowest value post-dose;
- SBP >90 mmHg;
- QTcF <500 ms and QTcF increase from pre-dose <60 ms;
- No persisting significant ECG abnormality (e.g., AV block second or third degree) or ongoing AE requiring continued cardiac monitoring or prohibiting study continuation as an out-patient.

If the subject does not meet the discharge criteria (as described above) at 4 hours post-dose, the subject should be carefully monitored for an additional period, and a 12-lead ECG and BP measurement must be performed every hour. The subject can be discharged from cardiac monitoring as soon as the above criteria are met.

Should the subject not meet the criteria for discharge from cardiac monitoring at 12 hours post-dose, she/he must be prematurely discontinued from study treatment. Subjects who are prematurely discontinued should not be discharged from cardiac monitoring before vital signs return to near baseline values in the extension study, or until there is no persisting ECG abnormality (e.g., AV block second degree or higher), ongoing AE requiring continued cardiac monitoring, or until medically indicated.

5.1.11 Premature discontinuation of study treatment

In the study, the premature discontinuation of study treatment is defined as a permanent discontinuation of study treatment earlier than the planned treatment duration of 240 weeks or ponesimod is commercially available. The decision to prematurely discontinue study treatment may be made by the subject, the investigator, or the sponsor.

A subject has the right to prematurely discontinue study treatment at any time by withdrawal from treatment only, or by withdrawal from treatment and any further participation in the study.

The investigator should discontinue study treatment for a given subject if, on balance, she/he believes that continued administration would be contrary to the best interests of the subject. In the event of clinically significant progression of the disease as judged by the investigator, the investigator should consider switching to another potentially more effective therapy, discuss alternative treatment options with the subject, and document the outcome of this discussion in the medical records.

15 March 2022, page 71/216

Confidential

EudraCT 2016-004719-10 EDMS-ERI-207656619

Premature discontinuation of study treatment may also result from a decision by the sponsor, e.g., in the event of premature termination or suspension of the study [see Section 9.3].

The main reason for discontinuation of study treatment, and whether the discontinuation of study treatment is the decision of the subject, the investigator, or the sponsor must be documented in the eCRF.

A subject who prematurely discontinues study treatment and withdraws consent to participate in any further study assessments is considered withdrawn from the study. Subjects who die or are lost to FU are also considered as withdrawn from the study. Withdrawal from the study and FU medical care of subjects withdrawn from the study is described in Sections 9.2 and 9.4, respectively.

In the event of premature discontinuation from study treatment due to any reason, the investigator should consider prescribing appropriate treatment for MS according to the local clinical practice and availability. The investigator should exercise caution when considering the switch to another immunomodulatory MS treatment.

5.1.12 Study-specific criteria for interruption / premature discontinuation of study treatment and management of clinically relevant events

5.1.12.1 Cardiovascular

Subjects must be prematurely discontinued from study treatment if:

- The following change in HR is observed at any time throughout the study, as documented by 12-lead ECG:
 - HR <30 bpm, or
 - HR <40 bpm is sustained for at least 1 hour and is associated with symptoms of bradycardia (e.g., syncope, dizziness, or vertigo), or
- QTcF >500 ms is observed at any time throughout the study, as documented by 12-lead ECG, or
- The subject does not meet the criteria for discharge from cardiac monitoring on Day 1, or on the first day of re-initiation of study treatment following drug interruptions, if applicable, after 12 hours post dose monitoring.

FU monitoring must be provided until the event leading to study treatment discontinuation resolves, the condition is stable, or the change is regarded as no longer clinically relevant.

Continuous ECG monitoring is recommended for subjects who meet study treatment discontinuation criteria related to bradycardia or other arrhythmia. Subjects who are permanently discontinued should not be discharged from the monitored setting before vital signs return to near baseline values in the extension study and until there is no persisting ECG abnormality (e.g., QT prolongation, AV block second degree or higher) or ongoing AE requiring (continued) cardiac

15 March 2022, page 72/216

EudraCT 2016-004719-10 EDMS-ERI-207656619

Confidential

monitoring, or until medically indicated. Any clinically relevant finding meeting the definition of an AE will be recorded accordingly in the eCRF.

In the event of any clinical signs or symptoms of bradycardia or other arrhythmia (e.g., syncope, palpitations, etc.), at any time during the study treatment, the first-dose administrator and/or a cardiologist may be consulted. If a cardiac origin is suspected, premature discontinuation of study treatment should be considered.

If subjects experience sustained *de novo* or worsening of pre-existing hypertension during the course of treatment with the study treatment which, in the opinion of the investigator, cannot be adequately controlled by medication, study treatment should be prematurely discontinued.

5.1.12.2 Hematological abnormalities

Subjects must be prematurely discontinued from study treatment at any time throughout the study in the event of:

• Confirmed total lymphocyte count $<0.2 \times 10^9/L$ ($<200 \text{ cells/mm}^3$)

Confirmation will be carried out as follows:

Whenever a total lymphocyte count $<0.2 \times 10^9/L$, is recorded by the central laboratory, an alert will be sent to the principal investigator and the sponsor. The principal investigator will immediately contact the subject and ask her/him to return to the site preferably within 48 hours but no later than within 1 week to repeat the test at trough level (pre-dose) with the central laboratory (unless the clinical situation mandates immediate local testing). If the repeat test confirms a total lymphocyte count $<0.2 \times 10^9/L$ the study treatment must be discontinued. Lymphocyte counts must be monitored at least once a week by the central laboratory until the lymphocyte count has returned to $\ge 0.8 \times 10^9/L$ or $\ge 80\%$ of the baseline value in the extension study. Any clinically relevant finding meeting the definition of an AE will be recorded accordingly in the eCRF.

In the event of a clinically relevant infection (e.g., opportunistic infection, serious infection), the study treatment may be interrupted and the subject referred to an expert in infectious diseases for further examination and treatment at the discretion of the investigator. In the event of study treatment interruption, the subject will be closely observed, and if the infection is resolved or not confirmed and the benefit/risk balance is considered acceptable for the subject to resume study treatment, the study treatment may be re-initiated at the discretion of the investigator.

In the event of premature discontinuation from study treatment due to infection, adequate treatment needs to be provided and the subject monitored until complete resolution of the infection.

A guidance for screening and monitoring of subjects for opportunistic infection is provided in Sections 5.1.12.2.1 and 5.1.12.2.2. Subjects must be advised to be proactive and alert in reporting

15 March 2022, page 73/216

EudraCT 2016-004719-10 EDMS-ERI-207656619

Confidential

any unusual neurological symptoms, and any signs and symptoms indicative of systemic infections, such as fever, malaise, and fatigue.

In the event of a suspected opportunistic infection in the CNS, unscheduled brain MRI scans may be performed at the investigator's request.

5.1.12.2.1 Guidance for exclusion and on-treatment monitoring of subjects for progressive multifocal leukoencephalopathy

Progressive multifocal leukoencephalopathy (PML) is an opportunistic infection of the CNS that can lead to death or severe disability. Active replication of the human polyoma John Cunningham Virus (JCV) in glial cells of the brain, causing lytic death in oligodendrocytes, is the underlying pathobiology of PML. The infection typically arises in severely immunocompromised subjects, e.g., those with HIV infection, malignant disease, or transplanted organs. Development of PML is extremely rare in immunocompetent individuals. People with autoimmune rheumatic diseases, especially systemic lupus erythematosus, are also at higher risk of PML [Kappos 2011].

MS subjects treated with natalizumab are at increased risk of developing PML. In addition to natalizumab, cases of PML have been reported in subjects treated with various drugs, usually in combination with corticosteroids, including alkylating agents (e.g., cyclophosphamide, carmustine, and dacarbazine), purine analogues (e.g., fludarabine, cladribine, and azathioprine), immunosuppressants (e.g., ciclosporin, tacrolimus, sirolimus, and mycophenolate), therapeutic monoclonal antibodies (e.g., rituximab, infliximab, etanercept, basiliximab, daclizumab, efalizumab, alemtuzumab, and muromonab-CD3) [Kappos 2011] and, in rare instances in subjects treated with fingolimod or dimethyl fumarate.

Clinical features indicative of PML are:

- Subacute onset;
- Occurs over several weeks and is progressive;
- Clinical presentation includes aphasia, behavioral and neurophysiological alteration, retrochiasmal visual deficits, hemiparesis, and seizures.

For subjects with prior exposure to natalizumab or other immunosuppressive agents who have been enrolled in the core study and who, under the study treatment, present new neurological symptoms suggestive of pathology other than MS, the investigator should consider PML or another opportunistic infection of the CNS and, in the event of clinical features indicative of these conditions, the following diagnostic procedures are recommended:

- Perform MRI including T1 sequences with Gd (and additional sequences if needed), and include comparison with the previous MRI images in the interpretation of the MRI results;
- Interrupt study treatment until PML or other opportunistic CNS infection has been excluded with confidence;

15 March 2022, page 74/216

Confidential

EudraCT 2016-004719-10 EDMS-ERI-207656619

Perform lumbar puncture and send cerebrospinal fluid (CSF) for JCV DNA testing by
polymerase chain reaction (PCR) with an ultrasensitive assay. The JCV DNA assay should be
based on quantitative real time PCR to maximize sensitivity and specificity for detection, and
an assay with a maximum lower limit of quantification of 50 DNA copies per mL should be
used.

Detection of JCV DNA in the CSF of a symptomatic subject confirms the diagnosis. However, a negative JCV PCR result should not exclude a possible diagnosis of PML.

If the CSF is negative but clinical signs and symptoms and/or MRI are still suggestive of PML:

- Consider repeating CSF analysis;
- Consider other opportunistic infections with CNS manifestations;
- Manage the subject on suspicion of PML or other opportunistic CNS infections according to local guidelines.

If,

- There are no suspicious signs of PML or other opportunistic infections on MRI and
- Lumbar puncture, if done, is negative for JC DNA, and
- The neurological signs and symptoms show improvement and are no longer suspicious of PML and can be explained by MS or an alternative, not infectious etiology,

the suspicion of PML is not supported. Other causes of the atypical neurological signs or symptoms or MRI findings need to be considered. Re-starting the study treatment should be considered if the benefit/risk is still favorable, according to the investigator.

However, if the investigator is still NOT able to rule out PML or another CNS opportunistic infection, the study treatment should be permanently discontinued, and the subject should be managed according to the local standard of care.

The PML cases should be reported to the sponsor as serious adverse events (SAEs).

If at the scheduled visit the MRI shows signs atypical for MS, PML or other opportunistic infection should be considered based on the clinical signs and symptoms, MRI results, previous exposure to natalizumab or immunosuppressants, and laboratory tests including CSF analysis, if indicated. As long as there is suspicion of PML or other opportunistic infection, the study treatment should be interrupted and should not be re-introduced until this suspicion has been ruled out.

5.1.12.2.2 General guidance for monitoring of subjects for opportunistic infections other than PML during treatment

Heightened vigilance is required for opportunistic infections, with particular attention to be paid to viral infections. However, investigators and physicians following subjects should also be alert to potential systemic infections caused by fungi and bacteria. In the event of an opportunistic

15 March 2022, page 75/216

EudraCT 2016-004719-10 EDMS-ERI-207656619

Confidential

infection, the subject must be referred to an expert in infectious diseases for further examination and treatment. The study treatment must be permanently discontinued in case of opportunistic CNS infections. For any other opportunistic infections, the study treatment may be interrupted or permanently discontinued at the discretion of the investigator.

It is important to recognize that opportunistic infections caused by the reactivation of human herpes viruses (herpes simplex viruses, varicella-zoster virus, Epstein-Barr virus, cytomegalovirus) may be associated primarily with neurological symptoms. The neurotropic herpes viruses (herpes simplex and varicella-zoster) are frequent human pathogens and their reactivation can cause serious infections of the CNS such as encephalitis and meningitis. The most frequent characteristics of these infections are an acute onset, associated with fever, headache, confusion, personality changes, and disorientation. Any suspicion of these infections must lead to immediate discontinuation of study treatment and to early initiation of antiviral treatment [Steiner 2007].

Particular vigilance is required for rare and unusual neurological symptoms, as their recognition is crucial for the early diagnosis of neurotropic herpes viruses infections.

The thorough physical examination and blood tests on the routine visits should be focused on any potential sign of skin, mucosal surfaces, gastrointestinal tract, liver, hematological etc, abnormality and organ dysfunction suggesting a potential opportunistic infection.

Subjects should be advised to be proactive and alert in reporting any unusual neurological symptoms and any signs and symptoms indicative of systemic infections, such as fever, malaise and fatigue [Kappos 2007].

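### A suspected herpes-type CNS infection is to be handled by interruption under two parts of Section 5.1.12.2 and by discontinuation, of unstated duration, under a third

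*Protocol*

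**What the plan says.** Three parts of Section 5.1.12.2 of the protocol govern treatment when an opportunistic infection is suspected or found.

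- **Section 5.1.12.2, opening text.** "In the event of a clinically relevant infection (e.g., opportunistic infection, serious infection), the study treatment may be interrupted", and referral to an infectious-disease expert is left to the investigator. After an interruption, "if the infection is resolved or not confirmed and the benefit/risk balance is considered acceptable for the subject to resume study treatment", then "the study treatment may be re-initiated at the discretion of the investigator". CNS infections are not excepted.
- **Section 5.1.12.2.1 (PML).** The diagnostic steps include: "Interrupt study treatment until PML or other opportunistic CNS infection has been excluded with confidence". For an atypical scheduled MRI it adds: "As long as there is suspicion of PML or other opportunistic infection, the study treatment should be interrupted and should not be re-introduced" until the suspicion has been ruled out. If PML or another opportunistic CNS infection cannot be ruled out, treatment is to be stopped permanently.
- **Section 5.1.12.2.2 (opportunistic infections other than PML).** "The study treatment must be permanently discontinued in case of opportunistic CNS infections". Other opportunistic infections may lead to interruption or permanent discontinuation, as the investigator judges. For herpes simplex and varicella-zoster infections of the CNS: "Any suspicion of these infections must lead to immediate discontinuation of study treatment". Referral to an infectious-disease expert is mandatory for any opportunistic infection.

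**The concern.** A subject with suspected herpes encephalitis has a suspected opportunistic CNS infection other than PML, and can fall under all three texts. Two of them describe an interruption that ends if the infection is excluded or not confirmed. The third requires discontinuation on suspicion alone and is silent on what follows a negative work-up. Two sites could handle the same false alarm differently, and each could point to the protocol.

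The setting is potentially life-threatening and the wording is mandatory, so consistency matters for patient management first. It also matters for the data. AEs leading to premature discontinuation are a listed safety endpoint (Table 9 and Section 11.4.8.1.3), and serious opportunistic infections including PML are a safety area of special interest (Appendix 4). How a suspected case is classified affects the first directly, and affects the exposure time around the second.

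**Working it through.** No sample size, power or event count is in question, so the check is a comparison of texts followed by the protocol's own timing rules.

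**Step 1: the instructions side by side**

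| Situation | 5.1.12.2 opening text | 5.1.12.2.1 | 5.1.12.2.2 |
|---|---|---|---|
| PML suspected | general rule for infections | interrupt; consider re-start if not supported; stop permanently if not excludable | outside its heading |
| Herpes-type CNS infection suspected | may interrupt | interrupt until excluded | discontinue at once; duration not stated |
| Same, then not confirmed | may re-start | no re-introduction until ruled out | silent |
| Opportunistic CNS infection confirmed, then resolved | may re-start; no CNS exception | no re-start rule for a resolved infection | permanent discontinuation |
| Referral to infectious-disease expert | optional | not stated | mandatory |

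The first row is coherent. The second and third hold the main conflict. The fourth and fifth are mismatches between a general and a narrower text.

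**Step 2: does the heading of 5.1.12.2.1 remove the conflict?** Not fully. It is headed PML, but its interruption rule and its rule for cases that cannot be excluded both extend to other opportunistic CNS infections. Its triggers are narrower: new neurological symptoms in subjects with earlier natalizumab or immunosuppressant exposure, or an atypical scheduled MRI. Outside those triggers the conflict is between the opening text of 5.1.12.2 and 5.1.12.2.2 alone.

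**Step 3: what does discontinuation mean in the herpes sentence?** The protocol points both ways.

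- Towards permanent: Section 5.1.11 defines premature discontinuation as permanent. Appendix 5 lists interrupting and discontinuing as alternative actions. The lymphocyte rule in 5.1.12.2 uses the bare verb for what it has introduced as premature discontinuation.
- Towards a stop of open length: the preceding paragraph of 5.1.12.2.2 adds the word permanently when it means that, and the herpes sentence does not. Section 8.5.4 uses discontinuation for a temporary pregnancy interruption, where 5.1.12.5 states the same 30-day rule with the word interruption.

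The sentence is therefore ambiguous. Only the permanent reading contradicts the interruption rules outright.

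**Step 4: what follows from each reading**

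- Interruption: the subject stays on the planned visit schedule off treatment (Section 3.2.3) for at most 12 weeks, that is 12 × 7 = 84 days (Section 5.1.8), and may then resume.
- Permanent discontinuation: the end-of-study visit falls 30 to 44 days later (Section 3.2.4), that is 30/7 = 4.3 to 44/7 = 6.3 weeks. This closes the efficacy period. The safety period closes at last dose plus 15 days, 15/7 = 2.1 weeks (Section 11.1.4.1).
- Later effect: Section 5.1.12.5 bars re-start after pregnancy if a criterion for permanent discontinuation was met at any previous visit. Whether an earlier suspicion counts as such a criterion therefore matters again.

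**The case against.** The strongest defence is that the texts differ in scope. The opening text is a general permission, and it refers the reader to 5.1.12.2.1 and 5.1.12.2.2, where the narrower rule for CNS infections is mandatory. A site can satisfy both by not using the permission in a confirmed CNS case. This largely stands for the confirmed or resolved case. What remains there is an omission: no exception is written, and the cross-reference describes the two subsections as guidance on screening and monitoring, not as overriding the re-start rule. For liver events the sponsor did write such a bar, in Section 5.1.12.6.

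The second defence is that the herpes sentence only means stop now. That would make it compatible with 5.1.12.2.1, and Section 8.5.4 shows that the word is sometimes used loosely. This stands as far as it goes: a contradiction on suspicion is not proven, but a mandatory instruction is left without a stated duration.

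Third, the infection does not drop out of sight after permanent discontinuation. Section 5.1.12.2 requires monitoring until complete resolution, and Sections 10.1.7 and 10.2.3 continue follow-up of ongoing AEs and SAEs. This stands. What ends is treatment and the scheduled assessments.

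A reader might infer that the protocol contradicts itself for every suspected opportunistic CNS infection, PML included. The documents do not support that, because 5.1.12.2.1 gives a complete sequence for PML. A reader might also infer that a false alarm could cost a subject most of the 240 weeks. Under Version 6 that cannot happen. The last subject entered on 20 May 2019 (Section 5.1.7) and Version 6 is dated 15 March 2022, about 147 weeks later. At most about 240 − 147 = 93 weeks remained, or 93/240 = 39%, and less for earlier entrants or where commercial availability ends treatment.

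**Conclusion.** The point holds in a limited form. For a suspected herpes-type CNS infection the protocol gives interruption with a possible re-start in two places, and in a third a mandatory discontinuation of unstated duration with no re-start path. The missing CNS exception and the difference on referral are secondary. The confirmed or resolved case is mostly a general permission narrowed by a specific rule.

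The size is small in numbers: few subjects are likely to be affected, all analyses are descriptive, and no stated figure changes. For an affected subject the difference is material, namely continued scheduled observation and possible resumption against end of study within about 4 to 6 weeks, and a different entry in the count of AEs leading to premature discontinuation. This contrast assumes that the herpes sentence is read as permanent. If it is read as temporary, what is left is the missing re-start rule, the missing CNS exception and the referral mismatch. This review takes no view on which clinical rule is right.

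**What to change.** Reconcile the opening text of 5.1.12.2 with 5.1.12.2.1 and 5.1.12.2.2:

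- Give one action for each situation (suspected, excluded, and confirmed or not excludable), using only the protocol's own terms, interruption or permanent discontinuation.
- State once whether and when treatment may be re-initiated, and once whether referral to an infectious-disease expert is optional or required.
- Add a cross-reference in the opening text of 5.1.12.2 to the rule for CNS infections.

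The sponsor decides which action applies in each situation. The cost is protocol wording, carried through a written amendment as Section 13.6 requires. No assessment or planned analysis has to change.
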